**RISK LEVEL****0 unresolved comment(s)**

Indicate which of the categories listed below accurately describes this protocol

- (Risk Level 1) Not greater than minimal risk
- (Risk Level 2) Greater than minimal risk, but presenting the prospect of direct benefit to individual subjects
- (Risk Level 3) Greater than minimal risk, no prospect of direct benefit to individual subjects, but likely to yield generalizable knowledge about the subject's disorder or condition.
- (Risk Level 4) Research not otherwise approvable which presents an opportunity to understand, prevent, or alleviate a serious problem affecting the health or welfare of subjects.

\*"Minimal risk" means that the probability and magnitude of harm or discomfort anticipated in the research are not greater in and of themselves from those ordinarily encountered in daily life or during the performance of routine physical or psychological examination or tests.

Refer to [UK's guidance document](#) on assessing the research risk for additional information.

**SUBJECT DEMOGRAPHICS****0 unresolved comment(s)**Age level of human subjects: (i.e., 6 mths.; 2yrs., etc.)  to **Study Population:**

Describe the characteristics of the subject population, including age range, gender, ethnic background and health status. Identify the criteria for inclusion and exclusion.

Provide the following information:

- A description of the subject selection criteria and rationale for selection in terms of the scientific objectives and proposed study design;
- A compelling rationale for proposed exclusion of any sex/gender or racial/ethnic group;
- Justification for the inclusion of vulnerable groups such as children, prisoners, adults with impaired consent capacity, or others who may be vulnerable to coercion or undue influence.

Please consider these resources:

[NIH Diversity Policy](#)

[FDA Diversity Guidance](#) 

Population will include adult ICU patients.

Inclusion criteria are as follows: AKI requiring RRT, with RRT being initiated within 48 hours of ICU admission.

Exclusion criteria are as follows: RRT of any type prior to ICU admission, underlying muscle disorders/atrophy, including quadriplegia or hemiplegia, history of stroke with residual muscle deficits, liver cirrhosis, alcohol dependence, active malignancy within 1 year, burns, or other baseline neuromuscular disease, pregnant patients, or anticipated inability to engage in weight-bearing testing after discharge (e.g., traumatic/orthopedic surgery).

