
## Objectives

List your research objectives. Please include a summary of intended research objectives in the box below.

Aim 1: Determine the rate and degree muscle wasting in critically ill patients with AKI-RRT vs historic ICU controls without AKI during ICU stay. Hypothesis 1: Patients with AKI-RRT have faster decline in rectus femoris and tibialis anterior muscle size compared to controls .

Aim 2: Determine the trajectory of muscle recovery in patients following an episode of AKI-RRT compared to matched controls by measuring muscle mass, muscle strength and power, and functional status in patients at discharge and at 1 and 3 months thereafter. Hypothesis 2: Patients with AKI-RRT will have a slower trajectory of muscle recovery following ICU discharge compared to matched patients without AKI.

Aim 3: Use trend analysis to determine that changes in plasma amino acid levels on RRT correlate with lean muscle loss during AKI-RRT and predict lack of muscle recovery at 1 and 3 months. Hypothesis 3: Trends in amino acid levels during treatment with RRT will correlate with MKUS determinations of lean body mass in the short-term and will predict lack of muscle recovery at 1 and 3 months.

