## Research Procedures

Describe how the research will be conducted.

- What experience will study participants have?
- What will study participants be expected to do?
- How long will the study last?
- Outline the schedule and timing of study procedures.
- Provide visit-by-visit listing of all procedures that will take place.
- Identify all procedures that will be carried out with each group of participants.
- Describe deception and debrief procedures if deception is involved.

Differentiate between procedures that involve standard/routine clinical care and those that will be performed specifically for this research project. List medications that are explicitly forbidden or permitted during study participation.

What RRT subjects will be asked to do/what happens in the study (in sequential order):

- Blood and effluent will be collected at the start of CRRT, at 48 hours, and on day 7 or ICU discharge, whichever comes first. The blood draw for research is 5 mL per draw.
- At hospital discharge, the patient will undergo a series of muscle strength and function tests including 1)Medical Research Council sum score (MRC-ss), a measure of global peripheral muscle strength that is the current clinical standard for diagnosing ICU-AW, 2) Maximal isometric knee extensor and dorsiflexion muscle strength measured as peak force production and rate of force development, and 3) Maximal isometric grip strength. Muscle power will be measured by the repetitive 5x sit-to stand test a reliable and validate measure of lower-extremity power. Physical function and frailty will be measured using 1) the Short Performance Physical Battery (SPPB), 2) six-minute walk test (6MWT), and 3) Clinical Frailty Scale. SPPB is a performance-based composite test with a total of 12 points including components of balance, chair to stand test, and 4-meter habitual gait speed.

The time period over which procedures will occur:

- Ultrasound will be completed at 2 time points: baseline (CRRT initiation) and 7 days after CRRT initiation OR ICU discharge (whichever comes first)
- Muscle strength/function will be assessed at hospital discharge, and at 1 and 3 months thereafter.

The time commitment for the subject for individual visits/procedures

- The time commitment will be 10-20 minutes for 2 ultrasound procedures as above, and the time needed to collect the research blood and effluent, which is likely to be <10 minutes daily for 7 days or until ICU discharge, whichever is first.

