- Muscle strength/function assessment is anticipated to take 30-60 minutes.

Long-term follow-up and how it occurs

- Patients will be seen at 1 and 3 months follow-ups in the outpatient setting. Visit times and dates will be arranged prior to discharge if possible, or via telephone after discharge.

Variables collected from the chart will include the following:

- Demographic data (Age, Gender, Race, BMI)
- SOFA or APACHE score at initiation
- Comorbidities (Charlson Score)
- Cause of AKI (Sepsis, post-surgical, etc.)
- Location of ICU (medical vs surgical)
- Laboratory data at baseline (BMP, CBC, lactate, albumin, INR)
- Daily laboratory data
- % Volume overload at initiation and daily
- CRRT variables (BFR, dose, therapy fluid flow rate, UF, filtration fraction).
- Reason for filter loss
- Time to death (censored for patient drop out or loss to follow up)
- In-hospital Mortality
- Time to renal recovery (censored for interfering events)
- Renal Recovery at hospital discharge

What Control subjects will be asked to do/what happens in the study (in sequential order):

- At hospital discharge, the patient will undergo a series of muscle strength and function tests including 1)Medical Research Council sum score (MRC-ss), a measure of global peripheral muscle strength that is the current clinical standard for diagnosing ICU-AW, 2) Maximal isometric knee extensor and dorsiflexion muscle strength measured as peak force production and rate of force development, and 3) Maximal isometric grip strength. Muscle power will be measured by the repetitive 5x sit-to stand test a reliable and validate measure of lower-extremity power. Physical function and frailty will be measured using 1) the Short Performance Physical Battery (SPPB), 2) six-minute walk test (6MWT), and 3) Clinical Frailty Scale. SPPB is a performance-based composite test with a total of 12 points including components of balance, chair to stand test, and 4-meter habitual gait speed.

The time period over which procedures will occur:

- Muscle strength/function and MKUS will be assessed at hospital discharge, and at 1 and 3 months thereafter.

The time commitment for the subject for individual visits/procedures

- The time commitment will be 10-20 minutes for ultrasound procedures as above, and muscle strength/function assessment is anticipated to take 30-60 minutes.

Long-term follow-up and how it occurs

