- Patients will be seen at 1 and 3 months follow-ups in the outpatient setting. Visit times and dates will be arranged prior to discharge if possible, or via telephone after discharge.

Variables collected from the chart will include the following:

- Demographic data (Age, Gender, Race, BMI)
- SOFA or APACHE score at ICU admission

Comorbidities (Charlson Score)

- Cause of respiratory failure (COPD, PNA, etc.)
- Location of ICU (medical vs surgical)
- Laboratory data at baseline (BMP, CBC, lactate, albumin, INR)
- Daily laboratory data

Patients lost to follow-up:

-We will attempt to contact patients prior to their appointment to remind them about the 1 and 3 month visits, and we will attempt telephone contact of patients lost to follow-up.

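### Aim 2: the only acute-severity score is timed at RRT initiation in cases but at ICU admission in controls, and the named tests carry no covariates

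*Protocol*

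**What the plan says.** Under Objectives, Hypothesis 2 is that AKI-RRT patients will have a "slower trajectory of muscle recovery following ICU discharge compared to matched patients without AKI". Study Design describes the study as non-randomised and has both groups measured at hospital discharge and at 1 and 3 months.

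The severity line in the chart list for RRT subjects (Research Procedures) reads "SOFA or APACHE score at initiation"; the line for control subjects reads "SOFA or APACHE score at ICU admission". Data Collection & Research Materials repeats the same split. No admission score is listed for cases. The Charlson score, listed for both groups, measures comorbidity rather than acute severity.

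The inclusion criterion is "AKI requiring RRT, with RRT being initiated within 48 hours of ICU admission".

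For comparing cases with controls, Study Design names independent t-tests and Mann-Whitney U tests at each timepoint and a two-way repeated measures ANOVA over time. It mentions no covariate and no matched-set term. The Protocol does not say whether matching is pairwise or by group, or on which variables.

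**The concern.** Without randomisation, severity of the acute illness is an obvious candidate to confound muscle recovery. A reader would look to this score to judge whether the groups were alike, and an analyst would reach for it to match or adjust. A value taken when RRT starts and a value taken at ICU admission do not describe the same point in the illness. Controls have no RRT initiation, so a later analysis plan cannot align the two unless the admission score is also abstracted for cases.

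The named tests then leave the Aim 2 contrast unadjusted. If the cases are sicker than their controls, an unadjusted comparison tends to favour the hypothesis of slower recovery. If a mistimed score is used for matching or adjustment and cases worsen between admission and RRT, they are set against controls who were sicker at admission, which works against the hypothesis. If cases improve over that interval, the bias reverses. The data as listed would not show which of these applies.

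**Working it through.** The Protocol gives no alpha, power, SD or effect size, so there is no figure to reproduce. Steps 1 to 3 rest on the text; steps 4 to 7 are illustrations with assumed inputs.

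**1. Anchors.**

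| | RRT subjects | Controls |
|---|---|---|
| Severity score | at initiation | at ICU admission |
| Scale | SOFA or APACHE, not fixed | SOFA or APACHE, not fixed |

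Initiation is best read as RRT initiation: the same list has volume overload at initiation and CRRT settings, and the ultrasound schedule equates baseline with CRRT initiation. The split appears in two sections, so it is not a single slip.

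**2. Gap.** From the inclusion criterion, a case's score is taken 0 to 48 h after ICU admission and a control's at 0 h. The gap can be zero for an individual case.

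**3. Tests.** None of the three named analyses contains severity, comorbidity or the matching.

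**4. If a mistimed score were used to match or adjust.** Assume cases change by 0.25 to 0.5 SD of severity before RRT, and severity correlates r = 0.3 to 0.5 with outcome. Bias = shift × r:
- 0.25 × 0.3 = 0.075 SD; 0.25 × 0.5 = 0.125 SD
- 0.5 × 0.3 = 0.15 SD; 0.5 × 0.5 = 0.25 SD

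Take a two-sided 5% t-test (noncentral t) and two assumed sizes: 30 v 30 (equal split of the maximum of 60) and 15 v 30 (cases halved, since Background puts in-hospital mortality above 50%).
- 30 v 30: 80% power needs 0.736 SD. If cases worsen, power falls to 71.1% (bias 0.075) or 45.6% (bias 0.25). If they improve, a true null is rejected in 5.9% or 15.9% of studies.
- 15 v 30: 80% power needs 0.906 SD. Power falls to 72.9% or 52.8%; the reversed case gives 5.6% or 12.1%.

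**5. If imbalance is left and nothing is adjusted, as the tests are named.** Bias = residual gap × r, with the same r. At 30 v 30 (normal approximation), the false-positive rate of a 5% test is:
- gap 0.25 SD: 6% to 8%
- gap 0.5 SD: 9% to 16%
- gap 1.0 SD (bias 0.3 to 0.5 SD): 21% to 49%

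**6. If matching is pairwise.** Let ρ be the within-pair correlation, assumed 0.2 to 0.4.
- 30 complete pairs: an independent test overstates the standard error by 1/√(1 − ρ) = 1.118 to 1.291. By simulation, a 5% test has true size 2.9% to 1.3%, and power is about 74.5% to 62.5% where a paired test has 80%.
- 15 cases and 30 controls with 15 intact pairs: the true variance is 1/15 + 1/30 − 2·15ρ/(15·30) = 0.1 − 0.0667ρ, against 0.1 assumed. The overstatement is √(0.1/0.0867) = 1.07 to √(0.1/0.0733) = 1.17.
- A paired test on those 15 pairs alone has variance 0.1333(1 − ρ). This exceeds 0.1 unless ρ is above 0.25, so dropping unpaired controls is no remedy.

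**7. Cost of adjusting.** Three covariates move the critical t from 2.0017 (58 df) to 2.0040 (55 df), or 0.1%, at N = 60. At N = 45 it moves from 2.0167 (43 df) to 2.0211 (40 df), or 0.2%. For equal groups with severity gap d, adjusted/unadjusted standard error = √((1 + d²/4)(1 − r²)). This is 0.87 to 0.98 for d = 0.25 to 0.5 and r = 0.3 to 0.5, and 1.07 for d = 1.0 and r = 0.3.

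**The case against.** The strongest reply is that this is an IRB application with a separate protocol file attached and not shown. Covariates, matching factors and the choice of scale are details that an analysis plan usually settles. That stands as far as silence goes: missing covariates alone would be a weak point. It does not answer what the document fixes, namely two different anchors and a named set of unadjusted tests. A later plan can add covariates, but it cannot make a score comparable that was recorded at different times.

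It is also fair that initiation is a coherent anchor for cases, since "Ultrasound will be completed at 2 time points: baseline (CRRT initiation) and 7 days after CRRT initiation" sets their baseline there and Aims 1 and 3 work from it. The score should therefore be kept. The chart lists are not closed either, so an admission score could still be added.

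Four stronger readings are tempting, and the documents do not support them.
- A reader might infer that the independent tests are simply wrong. The Protocol never says matching is pairwise. Under group matching no pairs are ignored, and under pairwise matching the error is conservative.
- A reader might infer that Aim 2 is biased by the mistimed score. Severity is never named as a matching or adjustment variable, and the named tests do not use it, so step 4 describes a possible use and not the plan.
- A reader might take 12% to 29% as the standard-error overstatement. That needs complete pairs; with half the cases lost it is about 7% to 17%.
- A reader might see a further mismatch in "Cause of AKI (Sepsis, post-surgical, etc" for cases against "Cause of respiratory failure (COPD, PNA, etc" for controls. It is not a defect: Aim 2 controls have no AKI, so no cause of AKI exists for them.

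**Conclusion.** The point holds in a limited form. Followed as written, the Protocol yields no acute-severity score comparable between groups and an unadjusted Aim 2 contrast in a non-randomised study of at most 60 subjects. From the text alone, the size is a timing difference of 0 to 48 h and an unfixed scale. Everything beyond that is illustrative and rests on assumed shifts, correlations and group sizes. At the low end the effect is small (bias 0.075 SD, false-positive rate about 6%); at the upper end of the mistiming range it is material (bias 0.25 SD, power 46% instead of 80% at 30 v 30). The direction cannot be determined from the document. This should be corrected, with medium confidence in its practical importance; it does not invalidate the study.

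**What to change.** - Name one severity score and abstract it at ICU admission in both groups. Keep the initiation score in cases as an additional variable.
- State whether Aim 2 matching is pairwise or by group.
- Make the main Aim 2 between-group comparison a repeated-measures (mixed) model with group, time and their interaction. Adjust it for a short prespecified list: age, admission severity and Charlson score. Include a matched-set term only if matching is pairwise, and use all available cases and controls rather than intact pairs only.
- Keep the t-tests, Mann-Whitney tests and unadjusted ANOVA as descriptive.

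The cost is one extra chart-abstracted score per case, a few sentences of text and about 3 degrees of freedom. Daily laboratory data are already listed for both groups, so part of an admission score may already be in the abstraction. At modest severity gaps the adjusted intervals would be slightly narrower. If the groups differ greatly on severity they would be somewhat wider, about 7% at a gap of 1.0 SD with correlation 0.3.

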**Short Title Description**

Please use a few key words to easily identify your study - this text will be displayed in the Dashboard listing for your study.

RRT and CIM

Anticipated Ending Date of Research Project: 9/30/2023

Maximum number of human subjects (or records/specimens to be reviewed) 60

After approval, will the study be open to enrollment of new subjects or new data/specimen collection?  Yes  No

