Acute skeletal muscle wasting is a common consequence of critical illness that occurs in up to 65% of patients admitted to the ICU. Critical illness myopathy (CIM), defined as a deficit in muscle size and strength that develops as a result of an ICU admission, is associated with high rates of short- and long-term morbidity and mortality, including decreased quality of life (QoL) due to persistent functional mobility impairments and inability to perform simple activities of daily living. Muscle dysfunction in the critically ill population is driven by underlying changes in cellular and molecular mechanisms leading to a net catabolic state. Rapid reductions in skeletal mass and strength lead to an increased risk of poor patient outcomes, including physical disability and mortality. The diagnosis of CIM in patients with acute respiratory failure or traumatic injury significantly increases the risk of in-hospital and long-term mortality. Recent data suggests that patients lose, on average, 19-27% of rectus femoris muscle size in the first ten days of critical illness. Little is known, however, about the significance of these changes in a subset of critically ill patients with acute kidney injury (AKI) requiring renal replacement therapy (RRT), also known as dialysis. The gold standard for assessing CIM is measurement by muscle biopsy or the analysis of psoas muscle area on a single cross-sectional CT imaging at the level of the L3 vertebra. Musculoskeletal ultrasound (MKUS), a non-invasive alternative, has gained significant traction over the last decade for assessing muscle in patients with critical illness. Studies have demonstrated that MKUS has excellent inter-rater reliability and high clinical utility, and have suggested that MKUS has strong construct validity. Recent data suggests that MKUS can be reliably performed at the ICU bedside, and our preliminary data suggests that graduate students in a healthcare-related field can reliably be trained to assess muscle mass in the ICU using MKUS in as little as 8 hours of training. Changes in rectus femoris size and quality (echo intensity) measured by MKUS were strongly correlated to muscle biopsies in patients with critical illness. In addition, MKUS measures have been shown to have clinical relevance. In a study of 102 surgical ICU patients, muscle wasting determined by MKUS was associated with increased rates of mortality and skilled nursing facility discharge. Acute kidney injury (AKI) is a commonly encountered condition that complicates 22.7% of all inpatient hospital admissions. More than half of all ICU admissions develop AKI, and 13.5% of all ICU patients will require renal replacement therapy (AKI-RRT) during their ICU stay. AKI is associated with poor short- and long-term prognosis. Even Stage 1 AKI is associated with a 10-fold increase in hospital mortality, and AKI-RRT has an in-hospital mortality rate >50%, making AKI-RRT one of the deadliest patient conditions encountered in U.S. hospitals. Even after discharge, patients with AKI continue to have worse outcomes. A meta-analysis of two million patients evaluating outcomes at least a year after admission showed that in-hospital AKI increased the risk of death. Despite how commonly AKI is observed and despite poor long-term outcomes, the rate of outpatient follow-up in this cohort is low. Therefore, patients with AKI are a high-risk, but underserved, group of patients that warrant further study and intervention. AKI of any stage is known to alter tissue utilization of amino acids. Studies have demonstrated that amino acid levels are reduced in AKI, and multiple, non-essential amino acids become conditionally essential. In addition, AKI leads to a state of increased amino acid oxidation, but reduced amino acid transport into muscle. Use of RRT may further exacerbate the issue by removing significant quantities of amino acids from the plasma. Amino acids are small and easily filtered during RRT, so daily losses of amino acids in effluent can be immense at up to 18 grams daily. While cross-sectional analyses demonstrate high clearance levels of amino acids during RRT, there are currently no published longitudinal data regarding amino acid levels. Because skeletal muscle is the major deposit of protein molecules, with nearly 60% of total body protein in humans, we hypothesize that patients with AKI-RRT are at even higher risk of CIM than critically ill controls without AKI.

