This is a prospective, non-blinded, non-randomized study to assess the impact of CRRT on critical illness muscle wasting. As the study is observational and non-interventional in nature, there will be no placebo administered in the course of the study. Patients will be identified based on conversations with ICU and Nephrology consult teams (in addition to chart screening) to determine which patients are likely to receive RRT therapy due to AKI and critical illness. In the first aim, patients will undergo musculoskeletal ultrasound (MKUS) assessments within 24 hours of CRRT initiation, and again at 48 hours and 168 hours. In addition, blood will be drawn at these timepoints and stored for later analysis. In Aim 2, the trajectory of muscle mass recovery will be determined through visits at the time of hospital discharge (to be completed within the hospital), and then at 1 and 3 months thereafter, which will entail separate visits. At these sessions, patients with AKI-RRT and matched controls will undergo measurements of muscle mass, strength, and function at hospital discharge and at 1- and 3-months following discharge. Measurements will include MKUS to determine CSA and muscle echogenicity in the RF and TA muscles. We will evaluate muscle strength by measuring: 1) Medical Research Council sum score (MRC-ss), a measure of global peripheral muscle strength that is the current clinical standard for diagnosing ICU-AW34, 2) Maximal isometric knee extensor and dorsiflexion muscle strength measured as peak force production and rate of force development38, and 3) Maximal isometric grip strength 40. Muscle power will be measured by the repetitive 5x sit-to stand test a reliable and validate measure of lower-extremity power. Physical function and frailty will be measured using 1) the Short Performance Physical Battery (SPPB), 2) six-minute walk test (6MWT), and 3) Clinical Frailty Scale. SPPB is a performance-based composite test with a total of 12 points including components of balance, chair to stand test, and 4-meter habitual gait speed. The 6-MWT assesses the distance a subject can walk in six minutes providing a global marker of physical function and representation of cardiopulmonary endurance. We will summarize descriptive statistics at each timepoint including mean and standard deviation or median and interquartile range, as appropriate. Independent t-tests and Mann-Whitney U tests for non-parametric data will be used as appropriate to compare differences in the testing outcomes between cases and controls at each timepoint. Two-way repeated measures ANOVA will be performed to assess the within change in muscle metrics over time and between group comparisons to understand the trajectories of muscle recovery.

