#### Benefits

- Describe potential direct benefits to study participants – including diagnostic or therapeutic, physical, psychological or emotional, learning benefits. This cannot include incentives or payments.
- State if there are no direct benefits.
- Describe potential benefits to society and/or general knowledge to be gained.

Describe why potential benefits are reasonable in relation to potential risks. If applicable, justify why risks to vulnerable subjects are reasonable to potential benefits.

Risk of blood draw will be minimized by drawing from RRT circuit once RRT is initiated. Accessing the dialysis circuit or arterial line for obtaining the research blood samples may increase the risk of infection. However, we will try as much as possible to combine these draws with labs that will be drawn anyway as part of routine RRT care, so additional risk should be minimal. Because ultrasound is a non-invasive imaging modality, risks of ultrasound are minimal. The risks of injury during assessment of muscle strength and function is minimal. There is a risk of loss of confidentiality, which we will minimize by using REDCap for data storage, and by removing identifying data as soon as the project is completed and published.

There are no direct benefits to the patient. The findings will not be communicated to the primary team, and will not be used to inform the patient's care in any way. With regards to society and general knowledge, AKI-RRT is a procedure with a very high rate of mortality (>50%). Patients who develop muscle loss after AKI-RRT initiation are at even further risk of morbidity and mortality. If AKI-RRT is shown to precipitate muscle loss due to amino acid removal, with slower rates of muscle recovery, this information can be used in future trials to study interventions such as the addition of amino acids to the dialysate/replacement fluid or early initiation of physical therapy/mobilization while on CRRT that would decrease sarcopenia development in this susceptible patient population, in order to

improve patient-centered outcomes.

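### Would the undefined censoring rule for time to renal recovery make the study overstate how many patients recover?

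*Protocol*

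**What the plan says.** The item appears in the chart-variable list for RRT subjects in the protocol's Research Procedures: "Time to renal recovery (censored for interfering events". The case-subject list in Data Collection & Research Materials repeats it. Neither place says what counts as interfering.

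Two lines above, the other time-to-event item does name its censoring reasons: "Time to death (censored for patient drop out or loss to follow up". In-hospital mortality stands between the two, and the list ends with a binary item, "Renal Recovery at hospital discharge".

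Background says that "AKI-RRT has an in-hospital mortality rate >50" per cent, and the Benefits text repeats the figure: "AKI-RRT is a procedure with a very high rate of mortality (>50" per cent.

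The analysis text is at the end of Study Design. It gives descriptive summaries, t-tests or Mann-Whitney tests at each timepoint, and for trajectories "Two-way repeated measures ANOVA will be performed to assess the within change in muscle metrics over time". No survival method is named. The three aims under Objectives cover muscle loss, muscle recovery and amino acids; renal recovery is in none of them.

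**The concern.** The two neighbouring items are worded differently. Time to death is censored for drop-out and loss to follow-up only, whereas time to renal recovery has a broader, open phrase. A reader will naturally suppose that the phrase takes in more than drop-out, and at the mortality the protocol quotes, death comes to mind first.

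Death before recovery is a competing event. Ordinary censoring assumes that a patient removed from the risk set could still have the event later, as those who remain can. A patient who has died cannot. If deaths are censored and one minus Kaplan-Meier is reported as the share who recovered, the figure answers what recovery would be if nobody died. It exceeds the real share whenever some deaths come before later recoveries.

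A second worry does not depend on the estimator. Three sites contribute, and without a definition they might code death, transfer or withdrawal differently.

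**Working it through.** The protocol gives no recovery rate, no timing and no figure for this variable, so there is nothing of its own to reproduce. The check asks how large the overstatement could be, and then whether the plan leads there.

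**Inputs.** Let d be the proportion who die before recovery, c the true proportion who recover, and r = c + d. The protocol's figure of more than 50% is general AKI-RRT mortality. It is not the share of this cohort dying before recovery: some patients may recover and then die, and the exclusion criteria shape who enters. So d is assumed at 30%, 40% and 50%, and c at 20%, 30% and 40%. No other censoring is assumed.

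**Constant hazards.** The total cumulative hazard is -ln(1 - r), and recovery's part of it is c/r. With deaths censored,

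1 - KM = 1 - (1 - r)^(c/r).

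For d = 0.5 and c = 0.3, r = 0.8 and c/r = 0.375, so 1 - KM = 1 - 0.2^0.375 = 0.453. The true value is 0.30, an excess of 15.3 points.

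| d | c = 20% | c = 30% | c = 40% |
|---|---|---|---|
| 50% | 29.1% (excess 9.1 points) | 45.3% (15.3) | 64.1% (24.1) |
| 40% | 26.3% (6.3) | 40.3% (10.3) | 55.3% (15.3) |
| 30% | 24.2% (4.2) | 36.8% (6.8) | 49.7% (9.7) |

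Simulation under the same hazards with d = 0.5 and c = 0.3 agrees. With 30 patients the mean of 1 - KM is 0.459 against a mean true share of 0.304; with 60 patients it is 0.453 against 0.300.

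**Without constant hazards.** If every recovery precedes every death, 1 - KM equals c and the excess is zero. If every death comes first, 1 - KM = c/(1 - d). For d = 0.5 that is 0.2/0.5 = 40%, 0.3/0.5 = 60% and 0.4/0.5 = 80%, an excess of 20, 30 and 40 points. So at 50% dying, the excess can lie anywhere from 0 to 40 points over these recovery rates, depending on an event order the protocol does not give.

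**A cohort in whole numbers.** The protocol's ceiling is 60 subjects, with no split stated. Assume 30 RRT patients, of whom 15 die, 9 recover and 6 are unresolved. The crude share recovering is 9/30 = 0.30. If all recoveries come first, 1 - KM is 0.30. If all deaths come first, 15 remain at risk and it is 9/15 = 0.60. Over random orders it averages 0.452.

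**Does the plan lead there?** The overstatement needs three steps:

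1. Death is treated as an interfering event. The protocol does not say so.
2. A Kaplan-Meier curve is drawn for this variable. Study Design names no time-to-event method.
3. The complement of that curve is read as the proportion recovering. Nothing in the text proposes this. Censoring at death is also a valid step when the target is a cause-specific hazard.

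**Can the data be coded correctly as collected?** Yes, for death. A patient whose recovery time is censored and who has a matching time to death died before recovery. Those with neither event are truly censored. The proportion recovered by discharge needs no survival curve: it is the count from the binary item divided by all enrolled RRT patients.

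**The case for a change.** The best argument for raising the point is that this is more than silence. The protocol writes a censoring rule, writes it twice, and the rule cannot be applied as written. The item just above shows that the authors could name their reasons when they chose to. Death is the commonest obstacle to recovery that the protocol itself describes, the possible distortion is large, and a definition would cost one line in a data dictionary. The conditional claim is statistically correct.

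Much of this stands. The term is undefined in the text at hand. The lists contain no separate item for transfer, so site differences in coding transfer could not be undone from the listed variables in the way that differences in coding death could.

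What does not stand is the step from an undefined term to a biased result. The phrase is a parenthesis in a list of chart variables; it belongs to no endpoint definition or analysis rule. Spelling out censoring events and choosing between a cause-specific hazard and a cumulative incidence is work a protocol commonly leaves to the statistical analysis plan, which is not at hand. The text is also an ethics-board application that lists a separate protocol file among its attachments, and a definition may be there.

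**Conclusion.** No change to the plan follows. The concern is right that one minus Kaplan-Meier with deaths censored would overstate recovery. It does not show that the study will do this: each of the three steps needed is absent from the protocol. The excess of 9 to 24 points rests on an assumed 50% dying before recovery, assumed true recovery of 20% to 40%, constant hazards and no other censoring. It illustrates a known error and is not a property of this plan.

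The gap is one that analysts fill in the ordinary course. If a proportion recovering over time is ever reported, the usual treatment is a cumulative incidence with death as a competing event, and the listed variables allow it. Renal recovery is recorded only for RRT subjects and serves no stated hypothesis, so no conclusion under the three aims depends on how the term is read. This judgement would change if the analysis plan made renal recovery an inferential outcome and estimated it by Kaplan-Meier with deaths censored.
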